5.8. Evaluation of Success of Blinding

Because of the nature of the intervention, our ability to maintain blinding for most participants and study personnel is limited. However, the success of blinding is particularly relevant in the chart reviews that we plan for evaluating the primary outcome. We plan to use Bang's Blinding Index (BI)²⁰ in the context of chart reviews by including a single question on the chart abstraction form asking research coordinators to indicate whether they

1. Strongly believe this participant is in the intervention arm
2. Somewhat believe this participant is in the intervention arm
3. Somewhat believe this participant is in the control arm
4. Strongly believe this participant is in the control arm
5. Don't know

Counts of responses will be compiled in a 2x5 matrix and the BI computed using statistical software, e.g. the -blinding- module in Stata. The index ranges from -1 to 1, where 1 indicates complete lack of blinding, 0 perfect blinding, and -1 perfect opposite guessing. It can be used to detect a low degree of blinding, response bias and different behaviors in two arms. We plan to compute this index stratified by research assistant and overall, using point estimates and confidence intervals.

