4.5 Blinding Procedures

Because of the nature of the intervention, it is not possible to keep dyads blinded to the intervention. Administering a placebo emollient would not be possible as there are no active ingredients in the emollient itself. Using an emollient that has no barrier improvement properties would likely be irritating to the skin and unethical to use on

infants. The lack of participant blinding is compensated for by the objective nature of the assessment (clinician-assessed AD) and by the final assessment being made by a blinded assessor.

Clinic staff at participating clinics will not be informed by study staff of participant enrollment or study arm, primarily to maintain blinding. There is a risk that parents may disclose their treatment group to clinic staff. Clinicians and clinic staff will direct participants to follow study skin care recommendations as described in study materials. Clinic staff should continue to treat skin-related diseases as they arise. After chart audit is completed on participants, clinicians will be asked which randomization arm they believe was assigned to individual participants.

PBRN research coordinators will be blinded and will be responsible for infants' health record review to collect the primary outcome from the participating clinics. If the family has disclosed the randomization status to the clinician, this information may appear in the health record. At completion of health record review, PBRN research coordinators will indicate which randomization arm they believe was assigned in order to measure whether the assessor became unblinded while reviewing the health record.

Maintaining integrity of randomization allocation and blinding is an important asset and will be maintained as a primary goal of the DCC. The principal investigator remains blinded during AE, SAE and UP assessment. DCC study personnel will be unblinded. CCC research assistants may become unblinded during conversations with participants during consent and enrollment, quarterly surveys, annual surveys, and in responding to incoming communications from participants.

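### The blinding index in SAP 5.8 uses guesses made after AD status is abstracted and is not split by AD status, so it cannot separate inference from the outcome from disclosure in the chart

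*SAP*

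**What the plan says.** Protocol 4.5 makes the practice-network research coordinators responsible for "health record review to collect the primary outcome from the participating clinics". It then says: "At completion of health record review, PBRN research coordinators will indicate which randomization arm they believe was assigned". The stated purpose is to learn whether the reviewer was unblinded by the chart, since a family may have told the clinician its allocation and the clinician may have written it down.

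SAP 5.8 puts the guess on the same form, "including a single question on the chart abstraction form asking research coordinators to indicate whether they" strongly or somewhat favour either arm, or do not know. "Counts of responses will be compiled in a 2x5 matrix", that is, arm by response. The analysis is: "We plan to compute this index stratified by research assistant and overall, using point estimates and confidence intervals". The scale is read as "where 1 indicates complete lack of blinding, 0 perfect blinding, and -1 perfect opposite guessing", and the SAP adds: "It can be used to detect a low degree of blinding, response bias and different behaviors in two arms".

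SAP 2.2 says that chart reviewers will also be asked whether they became unblinded. It gives no analysis for that question, which may be the same item as the one in 5.8. Neither document plans a split of the guesses by AD status or asks for the reason behind a guess.

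**The concern.** The trial's hypothesis is that emollient lowers the risk of AD. A coordinator who has just coded a child as having AD can guess control, and can guess intervention for a child without AD, while knowing nothing about allocation. Such guesses move each arm's index away from 0 with the blind intact. They can also cover up guesses that do rest on disclosure in the chart.

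Parents are unblinded, and Protocol 4.5 relies on blinded assessment to compensate. The coordinator index is the only blinding check with a planned analysis in the SAP. What is at stake is whether that check can answer its own question: did the chart reveal the arm?

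**Working it through.** **Inputs.** SAP 2.3 gives a control risk of 24%, an intervention risk of 16.8%, and 491 evaluable children per arm. SAP 3.3 gives 95% confidence intervals. The guessing rules below are assumptions, because the documents contain none.

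**Check of the plan's own figure.** SAP 5.8 states no figure for the index, so only the risks and sample size can be checked. With mean risk 0.204, two-sided 0.05 and 80% power:

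n = [1.960 × √(2 × 0.204 × 0.796) + 0.842 × √(0.24 × 0.76 + 0.168 × 0.832)]² / 0.072² = 490.5, or 491 per arm, as stated.

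**Index when guesses follow AD status only.** Per arm, the index is P(correct guess) − P(wrong guess). Let a share f of guesses follow the rule (AD: control; no AD: intervention) and let the rest be undecided.

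- Intervention: f × (0.832 − 0.168) = 0.664f
- Control: f × (0.24 − 0.76) = −0.520f
- Two-arm average: f × (0.664 − 0.520)/2 = 0.072f, which is f times the AD risk difference
- Variance per arm: (f − index²)/491; the variance of the average is one quarter of the sum of the two

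| f | Intervention (95% CI) | Control (95% CI) | Two-arm average (95% CI) |
|---|---|---|---|
| 100% | 0.664 (0.598 to 0.730) | −0.520 (−0.596 to −0.444) | 0.072 (0.022 to 0.122) |
| 50% | 0.332 (0.277 to 0.387) | −0.260 (−0.318 to −0.202) | 0.036 (−0.004 to 0.076) |
| 30% | 0.199 (0.154 to 0.244) | −0.156 (−0.202 to −0.110) | 0.022 (−0.011 to 0.054) |

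If all 625 charts per arm were guessed, the 50% average would be borderline (0.000 to 0.072, z = 1.99).

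**Other rules.**
- AD: control; no AD: undecided. Intervention −0.168, control +0.240.
- AD: strongly control; no AD: somewhat intervention, with an assumed weight of 0.5 for the weaker answer. Intervention 0.832 × 0.5 − 0.168 = 0.248; control 0.24 − 0.76 × 0.5 = −0.140.

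**No treatment effect (24% in both arms), f = 100%.** Arm values are +0.520 and −0.520; the average is 0.

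**A true leak.** If 10% of charts reveal the arm and all other answers are undecided, both arms show +0.10 (0.073 to 0.127). If the other 90% are guessed from AD status:
- Intervention: 0.10 + 0.90 × 0.664 = 0.698
- Control: 0.10 + 0.90 × (−0.520) = −0.368
- Unsplit average: 0.165

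The control value sits on the opposite-guessing side of the scale although one chart in ten disclosed the arm.

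**Same data split by AD status.** With no leak, the AD stratum gives −1 and +1 and the no-AD stratum gives +1 and −1, so the two-arm average is 0 in each. With the 10% leak, the AD stratum gives −0.80 and +1.00 and the no-AD stratum +1.00 and −0.80. The average is 0.10 in each, which is the true leak.

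**The case against.** - **Opposite signs give it away.** A leak affecting both arms alike pushes both indices up, whereas outcome-driven guessing pushes them apart. The SAP says that the index can show response bias and differing behaviour in the arms. This stands in part: a reader who looks at both arms could suspect response bias. The planned 2x5 table still could not tie it to AD status or reveal a leak mixed with it.
- **The extreme case is unlikely.** It needs every coordinator to guess by the outcome and nobody to be undecided. This stands, and it is why the range is shown. At 30% the arm intervals still exclude 0; the interval for the average does not.
- **A direct unblinding question exists (SAP 2.2).** It bears on disclosure and should be used, but no analysis of it is planned.
- **The timing is deliberate.** This stands. A guess made before the record is read could not detect disclosure within it, so the timing is not an error.
- **A split by AD status is not a complete cure.** This stands. Severity, treatments and skin-product events are in the same chart and can drive guesses too. Also, under SAP 5.1 uncertain records are adjudicated later by physicians, so the final AD status is not always what the guesser saw.

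A reader might infer that the false signal grows the better the emollient works. For the arm values this is largely wrong: they are ±0.52 with no effect, because most children have no AD. Only the average follows efficacy, and under outcome-only guessing it cannot exceed the risk difference of 0.072.

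**Conclusion.** The point holds as a limit on interpretation and a cheap improvement. As planned, the index mixes inference from the outcome with disclosure in the chart. The arm-level distortion could be material: about 0.2 in size if 30% of guesses follow AD status, and 0.5 to 0.7 if all do. It can also turn one arm's index negative in the presence of a real leak. These sizes rest on assumed guessing rules and on the planned risks.

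Two stronger readings are not supported. One is that the index would simply report failed blinding; that follows only if one arm is read alone, since the average is small and its interval includes 0 at 491 per arm when half or fewer of the guesses follow the outcome. The other is that the trial's main result is at risk. The diagnosis is made by clinicians, uncertain records are reviewed under blinding, and no decision rule depends on the index.

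**What to change.** In SAP 5.8:

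1. State that the index is reported separately for each arm.
2. Add a table of guess by true arm within AD status as the coordinator coded it at abstraction (Yes / No / Not sure), not the adjudicated status.
3. Report the association between guess and arm within those strata, for example with a Cochran-Mantel-Haenszel test, and state how undecided answers are handled.
4. Interpret blinding from this, the unsplit index and the SAP 2.2 unblinding question together. The stratified test should not be the sole basis.

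The cost is one table and one test on data already on the abstraction form. The AD-positive cells are small: about 84 and 120 children at 500 charts per arm (0.168 × 500 and 0.24 × 500). The split is therefore best done over all coordinators, not within each. Guesses driven by severity, treatment or skin-product events remain, and the text should say so.

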5.9. Missing Data

The approach to missing data will be guided by sources such as Jakobsen et al²¹ on missing data in randomized trials.

Definition of missingness in the primary outcome: The primary outcome, AD by 24 months of age, will be ascertained through review of medical records by research personnel blinded to intervention status and will be considered *not missing* if either (1) a diagnosis of AD is found for any visit before age 24 months (± 3 months), *or* (2) no diagnosis is found *and* the child had at least one visit in the 24-month window. The outcome will be considered missing if those conditions are not met, i.e. we

find no diagnosed AD before age 2 years *and* no clinic visit within ± 3 months of the child's second birthday.

COVID-19 pandemic as a cause of missingness: Because the primary outcome depends on an in-person clinic visit, it is likely to be missing for children who would otherwise have had visits during periods when the clinic was not offering in-person care or when parents declined to bring children for non-urgent care. The study team discussed extending the window for chart reviews to mitigate this effect, but this would require contacting parents for consent and was not adopted.

Missingness in other variables: Other variables from parent report will be considered missing if the response is absent or "don't know/unsure" or similar. In chart reviews, missingness will occur if a visit is not found, but if a visit is found, a "not found" for a particular category (e.g. medication) will be considered a non-missing "no." Validated multi-item scales will be scored according to published guidelines when available. When guidelines are not available, decisions about how to treat missing responses will be made and recorded before the dataset is locked for analysis.

If $\leq 5\%$ of observations are missing the primary outcome, then multiple imputation methods will not be of benefit and we will perform analysis without imputation. The treatment assignment, family history of atopic dermatitis, and recruiting clinic are assigned or used to create arm assignments and so will be complete for all participants.

If $>5\%$ of observations are missing outcomes, then further steps are needed. In addition to the analytic steps described here, we will discuss with members of the study team who interact with participants and clinic staff and may have insight into reasons for loss to follow-up that may or may not be reflected in recorded data. As a first step, we will create an indicator variable $R=1$ if the outcome is missing, $R=0$ if not missing. This variable R can be used to test whether missingness is associated with other variables, particularly:

- Study arm
- Family history of atopy
- Date of enrollment in study
- Parent report of AD
- Child's Eczema Questionnaire (CEQ) signs of AD
- UK Working Party criteria for AD
- PBRN

If differences are found (at $p < 0.10$, approximately, for an inclusive approach) then covariate-dependent missingness at least partly explains the missingness mechanism. Any such variable should be used in the multiple imputation model (or included in the main model without imputation) to produce unbiased estimates.

Multiple imputation will be performed using iterative chained equations over five (5) imputation sets. At the time of writing, the performance of multiple imputation when the model includes a random effect, such as the recruiting clinic in our model, is not well understood, and software to run the model we have proposed under multiple imputation is not readily available. (The estimation command is not available in Stata version 16, for example). Alternatives include (a) substituting a Poisson or logistic model, (b) omitting clinic, which should not be strongly associated with treatment outcome, or (c) Bayesian approaches, which could be especially useful if we suspect that data are missing not at random. The multiple imputation results will be considered the primary findings and will be reported along with complete case analysis.

5.10. Sensitivity Analyses

The sensitivity of findings to the choice of model and missingness assumptions will be addressed by some of the analyses already described, e.g. using different definitions for diagnosed AD in

secondary analyses, and conducting both complete case and imputed analysis. In addition, we plan to conduct "worst case" and "best case" analyses, and to calculate how many of the missing outcomes in the intervention arm would need to have AD in order for the point estimate of treatment effect to be null (RR=1).

The COVID-19 pandemic may affect the discovery of the primary outcome due to fewer office visits. We will examine potential changes over time in (a) missing primary outcome, i.e. no diagnosed AD and no primary care visit within the window of time for the 24-month assessment, and (b) the prevalence of the primary outcome in non-missing data.

Evidence also suggests that the incidence of respiratory syncytial virus (RSV) decreased during the pandemic, which may affect secondary outcomes related to wheezing. We will conduct a similar sensitivity analysis for a change in prevalence in RSV in the study population over time.

Additional sensitivity analyses may be identified as the datasets are prepared for analysis and before the breaking of the blind. Some accounting of the amount of emollient requested, for example, may be useful.

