4.7.3 Lost to Follow Up

A participant will be considered lost to follow-up if they have no documentation in the electronic medical record of AD and they have no 2-year visit data available given appropriate time windows.

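### SAP 5.10's trend in AD prevalence among non-missing children cannot be interpreted as a pandemic check, because its denominator depends on the 24-month visits whose loss it is meant to assess

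*SAP*

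**What the plan says.** SAP 5.9 defines when the primary outcome is observed, and there are two routes. The first is that "a diagnosis of AD is found for any visit before age 24 months", with a 3-month allowance. The second applies to children whose chart shows no AD, and it requires that "the child had at least one visit in the 24-month window". Protocol 4.7.3 uses the same asymmetry for loss to follow-up: a participant is lost only with "no documentation in the electronic medical record of AD and they have no 2-year visit data available".

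SAP 5.9 expects the pandemic to act through visits. It says of the primary outcome that "it is likely to be missing for children who would otherwise have had visits during periods when the clinic was not" seeing patients in person. A longer chart-review window was considered, but "this would require contacting parents for consent and was not adopted".

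SAP 5.10 then states that "The COVID-19 pandemic may affect the discovery of the primary outcome due to fewer office visits" and plans to track two quantities over calendar time. Check (a) is the frequency of children without an outcome, described as "missing primary outcome, i.e. no diagnosed AD and no primary care visit within the window of time for the 24-month assessment". Check (b) is computed only on the children who remain: "the prevalence of the primary outcome in non-missing data". The section does not say that (b) depends mechanically on (a), and it plans no correction or common denominator for (b).

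**The concern.** Under the 5.9 rule only undiagnosed children can be missing. Measure (b) keeps every charted case but keeps undiagnosed children only if they attended around their second birthday. Its denominator therefore shrinks with the visits whose loss is being studied.

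Two forces act on (b). Lost 24-month visits remove undiagnosed children and raise it. Lost earlier visits remove diagnoses and lower it. One reported trend combines the two. A rise could be read as more AD when only attendance changed, and a flat line could hide a real loss of diagnoses. The risk is concrete: the SAP revision history (version 3.0) records that chart auditors had already noticed many children with visits around 18 months who may have none around 24 months.

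**Working it through.** **Plan's own figure.** The documents give no number for this check, so I first confirmed the incidence inputs. SAP 2.3 uses 24% versus 16.8%, two-sided 0.05, 80% power, 1:1. The pooled two-proportion formula gives [1.960·√(2·0.204·0.796) + 0.8416·√(0.24·0.76 + 0.168·0.832)]² / 0.072² = 490.5, i.e. 491 per arm and 982 in total, matching the SAP. The average incidence over the two arms is (24% + 16.8%)/2 = 20.4%.

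**Set-up.** Let e be the share diagnosed before the 24-month window, l the share first diagnosed at the window visit, and v the probability of a window visit among children not yet diagnosed. Under SAP 5.9:

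- (b) = (e + l·v) / (e + (1 − e)·v)
- missing share = (1 − e)·(1 − v)

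The derivative of (b) in v has the sign of e·(l − (1 − e)). This is negative whenever some children are diagnosed early and some never are. With e and l fixed, a fall in v therefore always raises (b), even though the late diagnoses are lost along with the visit.

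**Size with true incidence fixed at 20.4%.** The values of v and the early/late split are assumptions; the documents give neither.

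| v | Missing share (all diagnoses early) | (b), all diagnoses early | (b), half first made at window visit |
|---|---|---|---|
| 1.0 | 0% | 20.4% | 20.4% |
| 0.9 | 8.0% | 22.2% | 21.3% |
| 0.8 | 15.9% | 24.3% | 22.4% |
| 0.7 | 23.9% | 26.8% | 23.7% |

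For example, at v = 0.9 with all diagnoses early: 0.204 / (0.204 + 0.796·0.9) = 0.204/0.9204 = 22.2%.

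At the plan's own loss of about 20% (SAP 2.3), with all diagnoses early, v = 1 − 0.20/0.796 = 0.749 and (b) = 0.204/0.80 = 25.5%. Moving from v = 0.9 to that level shifts (b) by 25.5 − 22.2 = 3.3 points with no change in AD.

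**The opposing force.** Suppose v falls from 0.9 to 0.7 and earlier visits also fall, so that some early diagnoses are never made. (b) stays at 22.16% if the early-diagnosed share becomes 0.2216·0.7 / (0.7784 + 0.2216·0.7) = 0.1662. That is 1 − 0.1662/0.204 = 18.5% fewer early diagnoses. A larger loss reverses the trend: with 30% fewer (e = 0.1428), (b) = 0.1428 / (0.1428 + 0.8572·0.7) = 19.2%.

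**Effect on the treatment comparison.** With all diagnoses early and the same v in both arms, the complete-case RR at v = 0.75 is [0.168/(0.168 + 0.832·0.75)] / [0.24/(0.24 + 0.76·0.75)] = 0.2121/0.2963 = 0.716, against a true 0.70.

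**The case against.** The strongest reply is that (b) is descriptive and does not stand alone. SAP 5.10 sets no test, threshold or decision on it. Check (a) is in the same sentence, so a careful reader sees the missingness shift beside the prevalence shift. If more than 5% of outcomes are missing, SAP 5.9 also tests date of enrolment as a predictor of missingness. The parent-questionnaire definitions of AD, the 18-month endpoint and the best-case, worst-case and tipping-point analyses give further protection.

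Much of this stands, and it limits the point. A reader might infer that (b) is the plan's only look at pandemic-era ascertainment. It is not: (a) and the enrolment-date test also use calendar time. Neither corrects (b), however. The enrolment-date test feeds the imputation model or the main model for the arm comparison, while (b) is explicitly computed on non-missing data. The questionnaire definitions, the 18-month endpoint and the best- and worst-case analyses are not planned by period.

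A reader might also infer that (b) must rise during the pandemic. That holds only if pre-window diagnoses are unchanged. SAP 5.10 itself expects fewer office visits to affect discovery of AD, and that pushes (b) down.

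Finally, one could pick a harsher fall in attendance. From v = 0.9 to 0.6, with all diagnoses early, (b) goes from 22.2% to 29.9%. But v = 0.6 implies 0.796·0.4 = 32% missing, well beyond the planned 20%, so that figure should not be the headline.

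**Conclusion.** Check (b) as defined cannot tell a change in AD from a change in attendance, and the net trend can be up, flat or down whatever happened to AD. The asymmetry follows from the SAP's own definitions and needs no assumption. The size does: with 20.4% incidence and all diagnoses made before the window, the artefact is about 3.3 points between a 90% visit rate and the planned 20% missing. It is smaller if many diagnoses are first made at the window visit, and it is cancelled or reversed if enough earlier diagnoses are lost.

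A reader might go further and infer that the treatment RR is materially biased. The documents do not support that. If visit rates are equal by arm, the complete-case RR moves only from 0.70 to about 0.716, and the primary analysis imputes when more than 5% are missing. The problem lies in the pandemic check and in absolute risks read from non-missing children.

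**What to change.** Replace (b) in SAP 5.10 with a measure that does not require a 24-month visit: cumulative incidence of charted AD by enrolment period, taken from the interval-censored or Kaplan-Meier onset analysis already planned (SAP 5.1 item 10, SAP 5.4 item 9), with AD-free children censored at their last charted visit, as Protocol 10.4.4 already provides for time to onset. A simpler alternative is diagnoses made before the window divided by all randomized children, which does not move when only 24-month visits change. Report the chosen measure beside (a), by the same periods.

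The text should also say that the replacement can still fall when fewer visits mean fewer diagnoses. It removes the artefact from the 24-month denominator, not the loss of ascertainment.

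The RR by enrolment period may be added, but as an optional, descriptive item only: SAP Table 1 puts power for the planned interactions at 0.36 to 0.65 even at the 0.1 level.

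The cost is a change of SAP wording and a little more programming, since the diagnosis, visit and enrolment dates are already needed for other planned analyses. Intervals by period will be wider. SAP 5.10 leaves room for further sensitivity analyses before the blind is broken, so the change fits within the existing plan if made by then.
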